## SYNOPSIS

Title of Study	Wearable Technology to Reduce Risk of DVT and Increase Patient Compliance
Objectives	
Primary: Conduct a randomized comparative study of DVT prophylaxis using either standard IPC (Group 1) or the RF MAC system (Group 2) in 300 patients after TJR surgery.
 
Hypothesis 1: During the in-hospital portion of the study, participants who use the RF MAC will have at least a 25% higher adherence rate of wear time of a fully operational IPC device than those using standard IPC devices (control group).
 
Hypothesis 2: Patients wearing the RF MAC in the first 24 hours following surgery will take at least 25% more steps as measured by an activity tracker than those patients using standard of care IPC devices.
 
Hypothesis 3: Patients who use the RF MAC will have a mean gait speed at 14 postoperative days that is at least 20% higher than patients receiving standard of care as measured by the 4-meter walk test.
 
Hypothesis 4: The time required for preparing patients to ambulate will be 50% less using the RF MAC than standard IPC devices.
 
Secondary: 1) Measure patient reported outcomes (PRO) of comfort, device acceptance and ease-of-use. 2) Collect feedback from nurses and physical therapists.

Planned Number of Subjects and Duration of Involvement	The total duration of the study is expected to be 18 months (recruitment, enrollment, participation, case closeout, analysis, completion of final report). This study will include two groups. Group 1 will serve as the control group and will receive standard care. Group 2 is the intervention group and will receive the RF MAC system pre-and post-operative care and standard mobility targets. Group 1 will consist of 75 patients at each of two sites (total of 150 patients). Group 2 will consist of 75 patients at each of two sites (total of 150 patients). Patients will be assigned to a group by a site Research Coordinator using a random numbers generator at their final pre-operative appointment.
Patient Population	This study will be conducted on Adult patients (age 40-85) who are scheduled for a first elective total hip replacement (THR) or first or second (opposite knee) elective total knee replacement (TKA). Patients will have an anticipated hospital length of stay of 48 hours or less and will be discharged to home from the hospital. Enrolled participants must be able to perform self-care, have a BMI of between 18 and 39 and a calf circumference between 11 and 24.5 inches

Investigational Products	RF Movement and Compressions (MAC) System including a charging hub, MAC controllers for each limb, and disposable MAC straps for each limb.
Methodology Overview	
Once IRB approval has been obtained, the sponsor team, [name] (University of Massachusetts) and Dr. [name] will begin training Research Coordinators at two study sites: Tufts Medical Center and Eskenazi Hospital. Research Coordinators will establish data collection methods (Case Report Forms) in REDCap (an online database for research data and surveys) at each site, RF MAC Systems will be shipped to the sites, charged and prepared for assignment to patients as they are enrolled in the study at their final pre-operative appointment. Each site will enroll 150 patients (300 patients total) and patients will be randomized in to one of two groups: Control (Group 1) or Intervention (Group 2). Participants will receive an identification number and all data collected will be password-protected. The study consists of two parts: in-patient and at-home. All participants will participate in both parts of the study.
 
In-Patient:
 
 
1. In the pre-operative appointment, the Research Coordinator will enroll participants and they will be randomly assigned to a study Group (control or intervention) and baseline information will be collected on the CRF.
 
2. A 4-meter walk test will be performed and the Research Coordinator will enter results in the patients CRF.
 
3. On the day of surgery, the patient will receive standard of care for each site for patients undergoing a THR or TKA. Patients in the control group (Group 1) will receive the site's standard of care IPC for DVT prophylaxis. Group 2 (intervention) will receive the RF MAC System for DVT prophylaxis. In addition, patients in both groups will receive an activity tracker.
 
4. In the first 24 hours post-operative, the Research Coordinator will visit the patient's room for observation a total of two times. During these visits, the Research Coordinator will visually observe the status of the DVT prevention device (control or intervention) to determine if it is properly applied to the patient's lower extremities and fully operational. This information will be recorded in REDCap. For Group 1 (control), this information will be collected by via observation by the Research Coordinator and patient interview. For the MAC System Group 2, this information will be collected automatically by the device and recorded by the Research Coordinator during the periodic visits.
 

5. Steps in the first 24 hours will be measured using an activity tracker. The Research Coordinator will record mobility data from the tracker to the CRF. Patients in Group 2 will also have steps measured automatically by the RF MAC System. The Research Coordinator will also record mobility reported by the RF MAC system in the patient's CRF.

6. At least once during the first 24 hours of the in-patient period, the Research Coordinator will measure through observation and using a stopwatch, the amount of time required by a nurse to prepare the patient to ambulate (removing tubes, cords, etc.).

7. Prior to discharge, the Research Coordinator will conduct a second 4-meter walk test. Results will be recorded in the patient's CRF.

8. As the patient is preparing for discharge, the Research Coordinator will ask the care team to complete a brief survey regarding their experience with both the standard DVT prophylaxis device and the RF MAC System during their hospital stay.

**At Home:** Once discharged, patients will continue involvement in the study at home. Patients in Group 2 will be sent home with their RF MAC System and a "patient packet" that includes a user manual, charging station, controllers, additional straps, a list of study contacts, a patient self-report journal, instructions for wear time and prescriptive mobility, and instructions for returning their devices and activity tracker at the end of the study. Patients in Group 1 will be sent home with instructions for the standard of care, and instructions on how to return their activity tracker. Patients in both groups will receive orders for standard of care from their healthcare team. This may or may not include IPC DVT prophylaxis for Group 1. Group 2 will receive orders for mobility and use of the RF MAC System. In addition, patients in both Groups 1 and 2 will receive daily at-home mobility goals from their healthcare team.

9. The Research Coordinator will record the prescribed at-home standard of care provided prior to discharge.

10. Patients in both groups will receive orders for at-home physical therapy for a minimum of 14 days, which is standard of care for TJR patients discharged to home.

11. Group 1 will receive standard of care DVT prophylaxis (which may be compression stockings, standard IPC or no orders) and a daily goal for steps (mobility). Compliance related to DVT prophylaxis will be self-reported by the patient in a journal in terms of total minutes per day. Compliance with mobility goals will be tracked using an activity tracker in addition to being self-reported.

	

12. Group 2 will receive instructions on how many hours per day to use the RF MAC System and a targeted number of steps to achieve per day (from healthcare team). Primary compliance data with DVT prophylaxis will be self-reported in a patient journal. Data related to mobility goals will be collected by the RF MAC System and recorded each day by the patient.

13. A final 4-meter walk test will be administered by the Research Coordinator at the 2-week in-office visit and results will be entered into REDCap.

14. At the end of the study, patients will complete a brief survey regarding their experience with both the standard DVT prophylaxis device and the RF MAC System during their in-home recovery. All participants will receive \$100 as remuneration for their study participation and be asked to sign a compensation receipt form. Participants at Tufts Medical Center will also receive \$21 for parking reimbursement.

15. The home physical therapist will also be asked to complete a brief survey.

--	--

# 1 INTRODUCTION

## 1.1 Overview: Deep Vein Thrombosis, Intermittent Pneumatic Compression and Circulation

Deep Vein Thrombosis (DVT) is a blood clot in a deep vein which occurs when venous blood flow is decreased. Lower extremity DVT requires immediate medical intervention, as it can cause a serious or fatal pulmonary embolus (PE). In the US, DVTs are a leading cause of preventable hospital death, affecting 350,000-900,000 patients and an estimated 60,000-100,000 annual deaths. DVTs are the fifth most common reason for hospital readmission, the third most frequent complication of total joint replacement (TJR), and is associated with an estimated annual cost of \$10 billion.

The risk of DVT is increased in hospitalized patients for a variety of reasons including, chemotherapy, surgery, and any condition that causes a general decrease in mobility. Immobility is one of the easiest modifiable risk factors for prevention of DVT. In fact, one recent study showed patients spend as much as 95% of waking hours in bed while they recover. In fact, DVT is the most feared complication of TJR, with more than 300,000 total hip and 700,000 total knee replacements performed annually in the U.S. Current recommendations for postoperative DVT prevention after TJR include anti-coagulant medications and/or external compression of the lower limb for a minimum of 10-14 days. Since the use of anticoagulants increases the risk of bleeding, if the same level of DVT prevention can be achieved with the use of external intermittent pneumatic compression devices (IPC), patients outcomes could be improved. The degree of enhanced blood flow, particularly in the femoral vein, is particularly important for effective DVT prevention, therefore, it is important to understand the blood flow enhancement efficacy of the available IPC products.

## 1.2 Impact of IPC on General Circulation

Some data support that the use of IPC can enhance blood flow throughout the body. Use of a laser Doppler flowmetry device has demonstrated that the use of an IPC that covered both the limbs and abdomen enhanced blood circulation to the forearms. In another study, participants who received IPC therapy for 30 minutes twice a day for two consecutive days achieved an average increase in mean arterial pressure of 5mmHg, a decrease in HR of 4bpm, a significant increase in peripheral vascular resistance index (from 545 [440-1066] to 613 [369-1280] dynes s cm(-5) m(-2) [P = 0.013]) and reduction in cardiac index (from 3.4 [2.7- 4.5] to 3.2 [2.5-4.0] L/min per m^2 [P = 0.034]).

A study using an IPC on the thigh was shown to increase levels of oxygenated hemoglobin in ischemic limbs of patients with severe peripheral artery disease. Traditional foot-calf IPC did not exhibit any associated increases in oxygenated hemoglobin. A similar study followed patients with critical limb ischemia that were considered amputation-bound. After use of IPC for 12 weeks, mean toe pressures increased from 38.2 to 67 mm Hg, popliteal artery flow velocity increased from 45 to

47.9 cm and cumulative survival at 12 months was 81.2% for IPC therapy users, compared with 69.2% in the control group. This study was repeated in 2011 and 2013 with similar results.

### **1.3 Impact of IPC on Femoral Vein Circulation**

Available data on femoral vein circulation support that circulation can be improved with IPC use. One study used both plantar-calf and calf IPC in healthy volunteers and found a significant increase in the maximum velocity of the femoral vein after just five minutes of use. Another study on healthy subjects using the most common type of IPC demonstrated an over 300% increase in average peak velocity in the common femoral vein of each limb after each compression cycle. In a group of inpatients getting prophylactic IPC status post total knee arthroplasty, ultrasonography found that blood volume and velocity was increased in both superficial and deep venous systems in the thighs.

## 2 DESCRIPTION OF THE INVESTIGATIONAL PRODUCTS

### 2.1 RF Movement and Compressions (MAC) System

The RF MAC System is a novel device that is applied to the lower legs of patients that provides intermittent active compressions to the calf muscles which results in increased blood flow in the veins, moving blood towards the direction of the heart and reducing the risk of clot formation.

The Movement and Compressions System is intended to be a portable and wearable system, prescribed by healthcare professionals, to treat the following conditions by stimulating blood flow in the legs:

- Aid in the prevention of DVT (deep vein thrombosis) by enhancing blood circulation; and,
- As a prophylaxis for DVT by persons expecting to be stationary for long periods of time.

During use, the system also monitors patient orientation and movement. It allows healthcare providers and users to implement individualized patient management plans for DVT prophylaxis and patient mobility protocols by utilizing data accumulated by the patient on the previous day as a benchmark. The data displayed on the device allows providers to monitor the patient's orientation, and activity, which can be used to identify risk factors for hospital-acquired events linked to immobility such as: deep vein thrombosis, pressure ulcers, pneumonia, atrophic muscles, and delirium.

The device can be used in the home or clinical setting. The device is intended for use in an adult patient population.

## **STUDY PURPOSE AND AIMS**

The primary purpose of this study is to conduct a multi-site clinical trial of the RF MAC System. The study involves two study sites: Tufts Medical Center (Boston, Massachusetts) and Eskenazi Hospital (Indianapolis, Indiana). This study is funded by a Phase II SBIR awarded to Recovery Force from the National Institutes of Health, National Heart, Lung and Blood Institute (R44-HL132624-02).

### **2.2 Primary**

Conduct a randomized comparative study of DVT prophylaxis using either standard IPC (Group 1) or the RF MAC system (Group 2) in 300 patients after TJR surgery.

Hypothesis 1: Study participants who use the RF MAC will have rates of adherence to wear time of a fully operational device that are at least 25% higher than those using standard IPC devices.

Hypothesis 2: Patients wearing the RF MAC in the first 24 hours following surgery will take at least 25% more steps as measured by an activity tracker than those patients using standard of care IPC devices.

Hypothesis 3: Patients who use the RF MAC will have a mean gait speed at 14 postoperative days that is at least 20% higher than patients receiving standard of care as measured by the 4-meter walk test.

Hypothesis 4: The time required for preparing patients to ambulate will be 50% less using the RF MAC than standard IPC devices.

### **2.3 Secondary**

Measure patient reported outcomes (PRO) of comfort, device acceptance and ease of use and measure nurse perceptions of device acceptance and ease of use and collect feedback from nurses and physical therapists.

## **4. STUDY OVERVIEW**

### **2.4 Study Approach**

Once IRB approval has been obtained, the RF study team will begin working with site Research Coordinators to implement the study. The initial phase will focus on planning and training, followed by enrollment of initial patients.

Once patient enrollment begins, each site will recruit a total of 150 patients (75 in control group and 75 in intervention group). Inclusion criteria includes adult patients (age 40-85) who are having their first elective total hip replacement (THR) or first or second (opposite knee) elective total knee replacement (TKA), speak English and are expected a hospital stay of two days or less with plans to discharge to home from hospital (not a rehabilitation facility). In addition, participants must be able to perform self-care, have a BMI between 18 and 39 and a calf circumference between 11 and 24.5 inches.

Exclusion criteria includes patients scheduled for a partial joint replacement, TJR revisions, emergency surgeries, those with calf deformities that would not allow proper fit for external compression devices, or patients who are non-ambulatory, clinically malnourished or frail/deconditioned. Finally, vulnerable patients (pregnant women, prisoners, homeless and cognitively impaired) and those that do not speak English are excluded from this study. Product labeling and materials are currently only available in English.

Table 1: Clinical Study Plan				
Site	Eskenazi Hospital		Tufts Medical Center	
Principal [name]		[name], MD & [name], MD	
Group (1 is Control; 2 is Intervention)	1	2	1	2
Targeted Enrollment	75	75	75	75
Total Targeted Enrollment per Site	150		150	
Total Projected Study Enrollment	300			

Each site will record the total number of patients screened, the number of patients excluded and the reason for the exclusion. These screening statistics will be reported to the Sponsor at the conclusion of the study.

### **Study Preparation:**

Training for implementation of the research protocol and all study procedures/documentation forms will be provided by [name], RN. Training for delivering the 4-meter walk test will be provided collaboratively by Drs. [name] and [name].

Product training for the RF MAC device for use in both the hospital and home will be provided to the Research Coordinators at each site by the RF clinical training team.

Study materials, including enrollment forms and surveys will be transferred to REDCap at each site. Each site will receive the following supplies:

- RF MAC Systems to meet patient enrollment goals
- Pedometers
- Waterproof bag for pedometers (worn around the neck)
- Stopwatch timers
- Digital height/weight and BMI scale
- Automated timing gates

- Electrical tape
- Gait belts
- Cones
- Measuring tape
- Measuring wheel
- Postage-paid packaging for returning devices

RF will be responsible for the shipping and installation of the RF MAC hardware. The additional single patient use leg straps will be shipped to each site by RF throughout the study to meet each site's enrollment cadence. The product must be stored in a cool, dry and locked location until they are distributed to participants. Each product package will include a User Manual and the MAC Solution brochure. Patients will also receive a paper journal for recording steps and use of the RF MAC System during the at-home study period.

**In-Patient:**

In the pre-operative appointment, the Research Coordinator will enroll participants and they will be randomly assigned to a study group (control or intervention). Patients will be assigned a participant number and that number will be recorded on their Informed Consent and the CRF. Only the Research Coordinators at each site and the PI will have access to the key that connects participant numbers to patient names.

A baseline 4-meter walk test will be performed and the Research Coordinator will enter results in the patients CRF. The protocol for the 4-meter walk test is described in the site protocols found in Appendix A (Tufts Medical Center) and Appendix B (Eskenazi Hospital).

On the day of surgery, the patient will receive standard of care for each site for patients undergoing a THR or TKA. Patients in the control group (Group 1) will receive the site's standard of care IPC for DVT prophylaxis. Group 2 (intervention) will receive the RF MAC System for DVT prophylaxis. In addition, patients in both groups will receive an activity tracker and corresponding waterproof pouch to hold the activity tracker. The display screen of the activity tracker will be covered with tape during the study period. Tape will be removed by Research Coordinators and data will be collected from the device at the end of the study period.

Research Coordinators will be responsible for providing device training to participants prior to discharge. This will be conducted using verbal explanation, demonstration and return demonstration. It is expected to require 10-15 minutes to complete training on the RF MAC System and review all required study materials, the use of the activity tracker and follow-up requirements.

In the first 24 hours post-operative, the Research Coordinator will record the total number of minutes that the DVT prevention device (control or intervention) was properly applied to the patient's lower extremities and fully operational. For Group 1, this information will be collected via patient interview and Research Coordinator observation. The Research Coordinator will visit the patient at least two (2) times in the first 24 post-operative hours and visually observe if the DVT devices are on the patient as directed by the standard of care, are fully operational and are correctly positioned. The Research Coordinator will note visual observations for each visit in the CRF. In addition, the Research Coordinator will ask the patient if they have kept their DVT devices on as directed by the healthcare team. The patient's response will be recorded on the CRF.

For Group 2, the MAC System will automatically capture time in use and display results on the device. Following the same protocol, the Research Coordinator will visit Group 2 patients at least two (2) times during the 24 post-operative period to observe if the RF MAC is in use, properly positioned (the device will not operate unless it is properly positioned) and will record the time displayed for DVT prophylaxis on the patient's CRF. In addition, the Research Coordinator will ask the patient if they have kept the DVT devices on as directed by the healthcare team. this information and results will be captured from the device display by the Research Coordinator and recorded in REDCap.

For both groups, steps in the first 24 hours will be measured using an activity tracker and the Research Coordinator will record this information in REDCap. For patients in Group 2, steps will also be measured automatically by the RF MAC System. The Research Coordinator will read the display screen on the MAC and record steps taken during the first 24 post-operative hours.

For both groups, at least once each day during the in-patient period, the Research Coordinator will measure through observation and using a stopwatch, the amount of time required by a nurse or other healthcare worker to prepare the patient to ambulate (removing DVT prophylaxis tubes, cords, etc.). The purpose of ambulation, time required to prepare the patient and time required to return the DVT prophylaxis will be recorded on the CRF.

Prior to discharge, the Research Coordinator will conduct a 4-meter walk test and record the results in REDCap and include a note of any assistive walking device used during the test. The Research Coordinator will also record the information on the display of the RF MAC at time of discharge (Group 2 only) and the number of steps on the activity tracker.

As patients in Group 2 are preparing for discharge, the Research Coordinator will coordinate survey completion for the patient and members of the care team (nurses, physical therapists, etc.).

Patients will receive at home orders for DVT prophylaxis, physical therapy and mobility goals. These orders will be recorded in the patient's CRF by the Research Coordinator. Group 1 will receive standard of care DVT prophylaxis (to be noted in the CRF) and Group 2 will take the RF MAC home to continue DVT prevention using the device.

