## 7 STATISTICAL METHODS

### 7.1 Determination of Sample Size and Planned Analyses

[name] (University of Massachusetts) is responsible for statistical design and power on this study. First, the team will test the group differences on demographic profiles and between RF1400 (Group 2) and standard-of-care (Group 1). If unbalances on any of these characteristics exist, the Horvitz-Thompson weights or propensity scores will also be adjusted to adjust for bias (d'Agostino, 1998). [name] will also compare the characteristics of the individuals who will drop out of the study with those who complete the study and create weights to adjust for any potential bias. For study, Recovery Force hypothesizes that the in-hospital outcomes measures (minutes of use in the first 24 postoperative hours, number of steps in the first 24 postoperative hours and the amount of

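### In-hospital wear minutes are read from a device display in Group 2 but built from interview and visit observation in Group 1, and the visit data shared by both groups have no planned between-group analysis

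*Combined protocol and SAP*

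**What the plan says.** Section 2.4, In-Patient, asks the coordinator to record "the total number of minutes that the DVT prevention device (control or intervention) was properly applied" and operational over the first postoperative day, in both groups. The source then differs by group:

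- Control: "For Group 1, this information will be collected via patient interview and Research Coordinator observation".
- Intervention: "For Group 2, the MAC System will automatically capture time in use and display results on the device".

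The same section also plans data that the groups share. Control patients are visited at least twice and checked for whether devices are "on the patient as directed by the standard of care, are fully operational and are correctly positioned". For the intervention, "Following the same protocol, the Research Coordinator will visit Group 2 patients at least two (2) times during the 24 post-operative period". The check made at these Group 2 visits is worded as follows: "observe if the RF MAC is in use, properly positioned (the device will not operate unless it is properly positioned"). Patients in both groups are asked essentially the same question; for Group 2, the coordinator will "ask the patient if they have kept the DVT devices on as directed by the healthcare team".

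The Synopsis (Methodology Overview, In-Patient step 4) gives the same split by source but sets the visits at two in total. It can be read as taking Group 2 device status from the device rather than by eye.

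Section 7.1 lists "minutes of use in the first 24 postoperative hours" among the in-hospital outcomes on which Group 2 is expected to do better, and treats every outcome as continuous. It names no analysis of visit status or of the interview answer.

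**The concern.** Hypothesis 1 is the first primary hypothesis. If its outcome is counted one way in one group and another way in the other, the estimated difference is the true difference plus the difference between methods, and randomisation does not balance the second part. Under-counting in controls relative to the display could produce an apparent benefit where none exists. Over-reporting by controls could hide a real one.

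The Group 1 inputs do not yield minutes directly. They are on/off status at a few moments and an answer about following instructions. In Group 2 the display accumulates time, and the device is said not to run unless correctly placed, so position and operation are built into its count.

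**Working it through.** **What the plan sets against this.** The weights in section 7.1 address baseline imbalance and dropout. The ANCOVA covariates are background and clinical variables. Section 7.2, on bias, covers only how patients are sampled. In the minutes data, method and group coincide exactly, so no term in the model can estimate one apart from the other.

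**The plan's own figure.** Section 7.1 states 130 per group for 0.35 SD, 80% power and 0.05. The normal formula 2 × ((1.960 + 0.842)/0.35)² = 128.2 gives 129, and the t-test solution is 129.1, rounded up to 130. The figure reproduces as two-sided (one-sided gives 102). With 150 per group overall and 15% dropout, 150 × 0.85 = 127.5 remain.

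**Effect of a method offset, equal SDs.** The offsets are assumptions; the documents give none. For a net difference of d SD, the chance of significance is P(|T| > critical value), where T is noncentral t with 2n − 2 degrees of freedom and noncentrality d√(n/2).

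| Situation | n per group | Net d | Noncentrality | Significant |
|---|---|---|---|---|
| No true difference, offset 0.1 | 127.5 | 0.10 | 0.798 | 12.5% |
| No true difference, offset 0.2 | 127.5 | 0.20 | 1.597 | 35.6% |
| No true difference, offset 0.1 | 150 | 0.10 | 0.866 | 13.9% |
| No true difference, offset 0.2 | 150 | 0.20 | 1.732 | 40.8% |
| True 0.35, no offset | 127.5 | 0.35 | 2.794 | 79.5% |
| True 0.35, opposite offset 0.1 | 127.5 | 0.25 | 1.996 | 51.1% |
| True 0.35, opposite offset 0.2 | 127.5 | 0.15 | 1.198 | 22.2% |

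The rows with 150 matter because the outcome is complete within 24 hours, before most dropout could occur. A larger sample makes the false-positive rate worse.

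**If Group 1 minutes are noisier.** Assume a wear fraction with mean 0.6 and SD 0.2 (288 of 1,440 minutes), so that 0.2 SD is 57.6 minutes. If Group 1 minutes came only from two independent spot checks, the within-patient correlation would be 0.04/0.24 = 0.167 and the SD 1440 × √(0.24 × 1.167/2) = 539 minutes. The standard error is √((539² + 288²)/127.5) = 54.1, and 57.6/54.1 = 1.064. The chance of significance in favour of Group 2 is then Φ(1.064 − 1.960) = 0.185. Simulation at 128 per group gives 0.18. The equal-SD figures are therefore at the high end.

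**Power of a visit-status comparison.** Assume two visits per patient and within-patient correlation ρ of 0.3 to 0.7. Effective n per group = 127.5 × 2/(1 + ρ), which is 196 to 150. With p̄ the mean of p₁ and p₂, power = Φ([|p₂ − p₁| − 1.96√(2p̄(1 − p̄)/n)] / √([p₁(1 − p₁) + p₂(1 − p₂)]/n)).

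| Assumed rates | ρ = 0.3 | ρ = 0.7 |
|---|---|---|
| 40% vs 50% | 51% | 41% |
| 50% vs 62.5% | 71% | 59% |
| 60% vs 75% | 89% | 80% |
| 60% vs 67% | 30% | 24% |

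The first three rows are 25% relative gains. The last is the plan's 0.35 SD if the SD is 288 minutes (0.35 × 288/1440 = 0.07).

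**A rule requiring both comparisons to be significant.** This was simulated 20,000 times at 128 per group, with beta-distributed wear (SD 0.2) and two independent snapshots. At 60% vs 67% with no offset, minutes alone succeed 79% of the time and both succeed 31%. With a 57.6-minute offset and no true difference, false conclusions fall from 36% to 2% if visit status is unbiased, but only to 13% if unblinded observers favour Group 2 by 5 points.

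**The case against.** The strongest reply is that the plan already collects comparable data: Group 2 visits follow the same protocol and both groups get the same question. That is correct, and a reader who inferred that no like-for-like measure exists would be wrong. What is missing is any stated between-group use of those data. The differences in visit criteria and in the source of Group 2 status are minor and may be wording only, since the Synopsis also speaks of visual observation in both groups.

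Second, no section says that Hypothesis 1 is tested on minutes. The Synopsis and section 2.2 word it as an adherence rate and give no denominator. This stands, so the link is an inference. Minutes are, however, the only in-hospital wear outcome in section 7.1.

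Third, a rule for deriving Group 1 minutes may sit in the CRF or in Appendices A and B, which were not available for this review. It cannot be said that none exists. Such a rule would still not make the two methods alike.

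Fourth, visit status is coarse and observed unblinded, and making it a second hurdle would remove more than half the power in the 60% vs 67% case. This also stands, and it is why a two-part rule is not asked for.

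**Conclusion.** The concern holds for the in-hospital minutes comparison. A significant result could not be attributed to wear rather than to method, and a null result would be equally ambiguous. This should be settled before analysis, and the visit criteria before further visits are recorded.

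The percentages show that a modest offset matters at this sample size; they do not estimate the offset in this trial. They rest on assumed offsets, two-sided testing and, except where stated, equal SDs.

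Two stronger readings are not supported. A reader might infer that the plan is biased in favour of the MAC, but the documents do not fix the direction. A reader might also extend the point to use at home. There, compliance with DVT prophylaxis is primarily self-reported in both groups (Synopsis steps 11 and 12; section 2.4, At Home, for Group 2), with the device display a secondary source in Group 2.

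**What to change.** 1. Beside the minutes analysis, pre-specify a between-group comparison of whether the device is on, correctly positioned and operational at each coordinator visit. Status should be observed by eye in both groups, with one set of criteria and matched postoperative visit windows. Analyse at visit level with clustering by patient and adjustment for site.
2. Report the minutes comparison as subject to differential measurement, with a sensitivity analysis over method offsets in both directions. Do not base the Hypothesis 1 conclusion on minutes without showing the visit comparison.
3. In Group 2, compare visit status with the displayed time as a descriptive check. The interview question yields no minutes and cannot be calibrated in this way.
4. Reconcile the Synopsis and section 2.4 on the number of visits and on how Group 2 status is obtained.

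Options for the sponsor, not required: a formal rule that both comparisons be significant, visit status as the primary endpoint, or an identical wear log in both groups.

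The cost is low: protocol, SAP and CRF wording plus some discipline on visit timing, with no new visits. The limits should be stated alongside. Two checks may miss the night, and power may be modest. Observer bias is also possible: an assumed 5-point bias (60% vs 65%) would by itself make visit status significant 14% to 17% of the time.
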